5.0 Selection and Randomization of Subjects

Participants

Men and women, aged 40-75 years, presenting to an orthopaedic surgeon with a full thickness rotator cuff tear will be eligible for study screening. The inclusion and exclusion criteria are listed below.

All eligible patients will receive information about the trial verbally and in writing. After signing written informed consent, they will be randomly allocated to undergo rotator cuff repair followed by standard of care structured rehabilitation with Oxandrolone administration or standard of care structured rehabilitation with placebo. Allocation will be performed using computer software and will occur at the pharmacy to ensure that all investigators are blinded. The USC Pharmacy will prepare sequentially numbered, opaque, sealed envelope containing the assigned interventions to ensure randomness is preserved. The surgeon, PI, study team, and physical therapist will not know to which study arm the patient was randomized. The protocol for rehabilitation will remain the same for all patients. The USC Pharmacy will provide the investigators with a list of all participants and group assigned at the end of the study. Investigators will not have access to the study group assignment for any participant during data collection, to ensure adequate double-blinding of both the investigators and participants.

Inclusion criteria

- Men and women age 40-75 years old who have failed nonoperative management of chronic, full thickness rotator cuff tears confirmed by MRI without contrast

Exclusion criteria

- Patients with prior shoulder surgery or prior rotator cuff repair
- Tears larger than 5cm
- Significant glenohumeral arthritis (Hamada Grade 2 or higher)
- Untreated diabetes mellitus
- Pituitary tumor
- Rheumatoid Arthritis
- Uncontrolled hypertension
- Congestive Heart Failure
- Myocardial Infarction within the past 6 months

- End-stage renal disease
- Liver enzymes two times the normal value
- DVT within the past 6 months
- Disorder of the coagulation system
- Currently taking anticoagulation
- Claustrophobia
- Prior or current use of anabolic steroids
- Chromosomal disorders
- Prostate cancer
- Breast cancer
- Hypercalcemia
- Medications that interfere with testosterone production or function, including but not limited to 5 α -reductase inhibitors
- Pregnant or breastfeeding, or expecting to conceive **or father** children within the projected duration of the trial, starting with the Screening visit through **6 weeks** after the last dose of study treatment.
- Any other condition or treatment interfering with completion of the trial

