1.0 Background

Rotator cuff tears are currently one of the most common causes of musculoskeletal pain and disability, and affect between 30% and 50% of the adult population over the age of 50 years.^{16,17} A torn rotator cuff can cause progressive loss of shoulder function and significant pain.^{4,5} The ramifications of rotator cuff tears are realized at both the individual and societal level where the direct costs of diagnosis and treatment and the indirect costs of loss of income, missed workdays, and disability payments continue to rise at exponential rates.^{17,18} The rate at which arthroscopic rotator cuff repair is being performed has increased by greater than 500% over the last 15 years.^{18,19} Given these high personal and societal costs, it is paramount to improve rotator cuff healing rates and decrease re-tearing and the need for reoperation.

Significant advancements in arthroscopic surgical techniques have led to a more stable mechanical environment to promote rotator cuff healing following repair.²⁰ Despite these major technical advances, there has been relatively slow progress consistently improving the biologic environment of healing tissues. This is especially true for rotator cuff repair where incomplete healing and re-tears remain a common postoperative complication. Studies suggest re-tear rates of up to 40% following small and medium tear repairs, and as high as 94% following for large and chronic tear repairs.^{21,22} Failure to heal the rotator cuff and rotator cuff re-tearing have clinical ramifications aside from the aforementioned societal and financial implications. Longitudinal clinical studies have demonstrated decreased functional improvement, diminished clinical outcomes, and lower patient satisfaction in those that have failure of healing or re-tears following rotator cuff repair.^{4,5}

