There are many predisposing factors that may prompt rotator cuff healing failure or re-tear. These factors can be divided into patient-specific factors (patient age, gender, body-mass index (BMI), smoking status, and comorbidities) and tear-specific factors (tear pattern, tear size, and tear chronicity).^{23,24} The major biologic sequelae of a constellation of both patient- and tear-specific factors are the changes to the muscle-tendon unit.^{7,25} The hallmarks of these changes are muscle atrophy, fatty infiltration, and intercellular fibrosis of the torn rotator cuff muscle-tendon unit.^{7,25} These changes begin at the time of the tear and currently go largely unaddressed at the time of repair.

Researchers have pursued biologic augmentation at the time of arthroscopic rotator cuff repair; however, time-zero modifications to the healing interface with growth factors, platelet-rich plasma, and stem cells have failed to address the hallmarks of the biologic problem (muscle atrophy, fatty infiltration, and intercellular fibrosis).²⁶ Therefore, these modalities in both preclinical and clinical models have failed to consistently demonstrate improvements in healing rates, re-tear rates, functional results, or patient satisfaction.²⁷⁻²⁹ Recently, researchers have attempted to address the biologic hallmarks of rotator cuff tearing with a series of animal studies examining the effects of anabolic steroids on rotator cuff healing.^{25,30,31} This line of preclinical studies demonstrated that anabolic steroids, when administered as an adjuvant to rotator cuff repair, can halt the progression of fatty infiltration, decrease muscle atrophy, and promote rotator cuff healing.

Despite the wide range of doses in controlled clinical trials, our proposed dose has not been studied. The drug manufacturer, Gemini Labs LLC, is providing the drug in 6mg doses for the study and the proposed oxandrolone dose in men is 24mg/day. Currently, the FDA-approved dose in adults is up to 20mg/day, usually in two to four divided doses. Most controlled studies use doses of 5–20mg/day.^{3,36} In patients with moderate to severe alcoholic hepatitis, however, doses have been given up to 80mg/day.³⁷ Adverse events are typically dose-dependent and correlate to the duration of use.³⁶ Serious hepatic toxicity has not been shown with short term (≤ 3 months) treatment of oxandrolone, even with up to 80mg/day.^{36,37}

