3.0 Study Design

Trial Design

This is a single-center, prospective 1:1 double blind randomized control trial. The trial will be conducted at the University of Southern California (USC), Keck School of Medicine in Los Angeles, California. Patients will be recruited from the Department of Orthopaedics. Men and women, 40–75 years of age, with MRI proven rotator cuff tears, indicated and scheduled for repair will be eligible for inclusion. Men and women with acute tears and those with significant comorbid liver, lung, cardiac, and kidney conditions will be excluded. Women who are pregnant or nursing will also be excluded. Women of child-bearing potential will be required to take a monthly urine pregnancy test and be on an agreed upon contraceptive. Participants will be randomized into one of two groups, a control group (receiving placebo medication) and an experimental group (receiving oral Oxandrolone, 12 mg twice daily for men and 6 mg twice daily for women for 12 weeks). Dosing will begin at the time of surgery and continue for 12 weeks, with medication dispensed by the USC Pharmacy. The study will be double-blinded: neither the treating surgeon nor the patient will know to which group the patient is enrolled.

Surgical Procedure

Arthroscopic inspection of the shoulder will be performed to verify the presence of a rotator cuff tear and to measure the size of the tear. In all cases a standard arthroscopic double-row technique will be used to repair the rotator cuff tendon.^{19,20} Treatment of the biceps tendon, need for subacromial decompression, and/or acromioclavicular joint resection will be at each surgeon's discretion. Intraoperative measurements of rotator cuff tear type and size as well as the details of the surgical procedure will be recorded.

Postoperative Rehabilitation

All participants in the study will undergo a standardized rehabilitation protocol for rotator cuff repair as agreed upon by the surgeons involved. Rehabilitation will be supervised by a licensed physical therapist. Adherence to the rehabilitation protocol will be assessed by review of patient treatment logs. If there are alterations to the standard postoperative rehabilitation course, the treating surgeon will be notified and will determine if the alteration in course warrants removal from the study. Patients who do not meet 80% adherence to the standardized protocol will be considered non-compliant and controlled for in the data analysis.

Feasibility

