6.0 Study Agent Administration and Safety

Oxandrolone Administration

Oxandrolone will be given to experimental men (12 mg BID) and women (6 mg BID) for 12 weeks starting the day of surgery. Previous clinical studies where oxandrolone was given for greater than 6 months have shown no androgenic effects, behavioral changes, sepsis, hirsutism, or acne in the patient population. Elevated liver transaminase levels have been noted but have been transient and asymptomatic.¹⁻³

Patient Safety and Compliance

Patients will have liver transaminase levels measured when preoperative labs are obtained. Additionally, liver enzymes will be assessed at 2, 6, 12, and 24 weeks after rotator cuff repair. Testosterone levels and a quantitative assay for oxandrolone will also be drawn prior to supplementation, at the 2 week post-operative visit and at the 6 month post-operative visit to assess for compliance. Any adverse medication reaction will be met with cessation of medication, but will continue to be followed for outcome data collection.

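### The primary GEE has no pre-specified baseline covariate and no stratification or blocking is described, although the protocol names tear size and gender as predictors of healing failure: a loss of precision, not a bias

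*Combined protocol and SAP*

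**What the plan says.** Section 3.0 (Trial Design) fixes the ratio: "This is a single-center, prospective 1:1 double blind randomized control trial". Section 5.0 (Participants) describes the mechanism: "Allocation will be performed using computer software and will occur at the pharmacy to ensure that all investigators are blinded", and "The USC Pharmacy will prepare sequentially numbered, opaque, sealed envelope containing the assigned interventions". Neither section mentions strata, block sizes or minimisation, and neither says how the sequence is generated beyond the use of software.

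The Background (1.0) lists gender among the patient-specific factors and tear size among the tear-specific factors that may lead to healing failure or re-tear. For tear size it cites "re-tear rates of up to 40% following small and medium tear repairs, and as high as 94% following for large and chronic tear repairs". Dose depends on sex: "Oxandrolone will be given to experimental men (12 mg BID) and women (6 mg BID) for 12 weeks starting the day of surgery" (6.0; the same in 3.0).

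Both factors are available before allocation. Tears are confirmed by MRI at entry, Section 7.0 lists tear size among the items recorded, and Table 1 places randomization on the procedure day.

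Section 10.0 analyses the Sugaya grade by a repeated-measures ordinal GEE and names no baseline covariate. The only adjustment mentioned anywhere is for poor adherence to rehabilitation (3.0, Postoperative Rehabilitation), which arises after randomization.

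**The concern.** The protocol identifies factors that it believes drive the primary outcome and collects them before treatment, but uses them in neither the allocation nor the analysis. In a trial of 116 patients, the proportion of large tears or of women can then differ noticeably between arms by chance. The unadjusted comparison also leaves the variation due to those factors in the error term.

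Two things are at stake. One is power, which could be raised without enrolling anyone else. The other is credibility: if a visible imbalance in tear size emerges, any adjustment chosen afterwards can be criticised as data-driven. A covariate set fixed in advance removes that criticism.

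**Working it through.** **Inputs from the documents (Section 10.0).** Difference of 1 Sugaya grade, SD 2, correlation 0.7, 3 repeated measures, two-sided alpha 0.05, power 80%, 52 per arm evaluable and 58 per arm enrolled.

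**Assumed inputs, because the documents give none.** Prevalence of the factor (women, or large tears): 20% to 50%. Effect of the factor on the Sugaya grade: 1 or 2 grades.

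**1. The plan's own sample size.** The variance factor for the mean of 3 measures is (1 + 2 × 0.7)/3 = 0.80, so the SD of the mean is 2 × √0.80 = 1.789. The noncentral F gives power of 79.8% at 51 per arm and 80.6% at 52. So 52 per arm (104 in total) reproduces, and 104/0.9 = 115.6, rounded up to 116, reproduces.

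**2. Chance imbalance if allocation is unstratified.** With arms of 58, the count of patients with the factor in one arm is hypergeometric. The SD of the between-arm difference in proportions is close to √(4p(1−p)/116).

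| Assumed prevalence | Patients of 116 | SD of difference | 95% range | Chance of ≥10 points |
|---|---|---|---|---|
| 20% | 23 | 0.074 | ±15 points | 16% |
| 30% | 35 | 0.086 | ±17 points | 22% |
| 40% | 46 | 0.091 | ±18 points | 34% |
| 50% | 58 | 0.093 | ±18 points | 35% |

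The step from 22% to 34% arises because counts are discrete. With 35 such patients, the smallest difference that reaches 10 points is 7 patients; with 46 it is 6.

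**3. Absence of blocking alone.** Under simple randomization of 116, the arms differ by 10 or more patients with probability 40%. A 63/53 split has relative efficiency (63 × 53)/(58 × 58) = 0.993, so unequal arm sizes cost almost nothing. The covariates matter more.

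**4. Effect on the test.** Simulation: 52 per arm, 10,000 runs, one binary factor at 30% prevalence, total SD held at 1.789, grade treated as continuous in a linear model.

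| Allocation and analysis | Type I error (1-grade / 2-grade factor) | Power (1-grade / 2-grade factor) |
|---|---|---|
| Unstratified, unadjusted | 0.051 / 0.049 | 81% / 81% |
| Unstratified, adjusted | 0.047 / 0.053 | 83% / 91% |
| Stratified, unadjusted | 0.041 / 0.021 | 82% / 85% |
| Stratified, adjusted | 0.049 / 0.046 | 83% / 90% |

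**5. Check by formula.** The unadjusted standard error is 1.789 × √(2/52) = 0.351, so the expected z is 1/0.351 = 2.85 and power is Φ(2.85 − 1.96) = 81%. The factor accounts for a variance of 0.3 × 0.7 × d², which is 0.21 for d = 1 and 0.84 for d = 2, out of 3.2. The residual fractions are 0.934 and 0.738.

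- Adjusted: z = 2.85/√0.934 = 2.95 and 2.85/√0.738 = 3.32, so power is about 84% and 91%.
- Stratified but unadjusted: the model's standard error is too large, and the true type I error is 2 × [1 − Φ(1.96/√0.934)] = 4.3% and 2 × [1 − Φ(1.96/√0.738)] = 2.2%.

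Both agree with the simulation.

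**The case against.** The strongest reply is that randomization is valid without stratification or adjustment, and that the usual standard error already allows for chance imbalance. That stands: type I error is about 5% in the simulation. A reader might infer that the primary result would be biased, and it would not be.

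Some protection also exists already. Tears over 5 cm are excluded, tear size is recorded so an imbalance would be seen, and baseline Sugaya grade enters the repeated-measures comparison. The last helps only in part, because Sugaya type V puts medium and large full-thickness tears together.

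Five stronger readings are tempting and are not supported:

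- *The plan uses one unstratified sequence.* The documents do not say so. They are silent on how the sequence is generated, and the imbalance figures apply only if allocation is in fact unstratified.
- *A single envelope series cannot serve two doses.* This does not follow. The manufacturer is "providing the drug in 6mg doses for the study", both doses are multiples of that unit, and the pharmacy performs the allocation. An envelope can carry the arm, and the pharmacy can dispense by sex.
- *The cited re-tear rates give the size of the error.* Multiplying an imbalance by the 54-point gap between 40% and 94% is not a fair measure. Both rates are maxima, the higher one is for large and chronic tears while this trial caps size at 5 cm, and the primary outcome is an ordinal grade. Any such shift also lies within ordinary sampling error. At an assumed 30% large tears those rates give 0.3 × 0.94 + 0.7 × 0.40 = 56% re-tear overall, and a 95% sampling range of 1.96 × √(2 × 0.56 × 0.44/58), about ±18 points.
- *Tear size is the strongest predictor.* The Background lists its factors without ranking them.
- *Stratifying by sex would make results interpretable by dose.* Dose and sex remain fully confounded under any allocation, and no dose comparison is planned.

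**Conclusion.** The point holds as an avoidable loss of precision, and as a gap in the description of allocation. Neither the allocation nor the primary model, as written, uses the two factors discussed here, although the protocol regards both as predictive and both are known before treatment. If allocation is unstratified, a 10-point imbalance arises in roughly a quarter to a third of trials at an assumed prevalence of 30% to 50%. The test stays valid.

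Adjustment raises power from 81% to about 83% if the factor is worth 1 grade, and to about 91% if it is worth 2. The gain is therefore small to moderate, and it depends on an effect that the documents do not give on the Sugaya scale. The simulation used a linear model, so the figures are a guide to the ordinal GEE, not exact for it. Nearly all of the gain comes from adjustment. Stratification adds little once the factors are in the model.

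**What to change.** In Section 10.0, pre-specify sex and tear size on the pre-operative MRI as covariates in the primary ordinal GEE, and state the form of tear size in advance (continuous, or categories with a fixed cut-off). In Section 5.0, state how the sequence is generated and whether it is blocked or stratified.

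Optionally, the pharmacy can use permuted blocks, with sizes concealed from the investigators, stratified by the same two factors. Tear size should then come from the MRI, because arthroscopic size is known only during surgery. As an illustration, blocks of 4 in four strata (sex by tear size) limit the difference between arms to 2 patients per stratum. That is at most 4 patients, about 7 points of 58, for either factor. If strata are used, both factors must be in the model, because stratifying without adjusting makes the test conservative (simulated type I error 2% to 4%).

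The cost is two model terms, plus a few more pharmacy lists if stratified. The planned 104 and 116 do not change. The treatment effect from the ordinal model becomes conditional on the covariates, which the analysis section should say.

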The study team has the experience, knowledge, and capability to conduct this study. The surgeons involved perform approximately 400 rotator cuff repairs per year. The study team assembled has conducted similar prospective studies in the past on rotator cuff healing. In addition, the study team has experience with clinical trials involving anabolic steroids.

The collaborative nature of the study is exemplified in the sharing of responsibilities. The majority of the clinical care proposed in this study (demographic data, medical history, physical examinations, vital signs, preoperative MRI without contrast) is standard-of-care treatment for rotator cuff tears all surgeons involved and will be overseen as such. The outcome measures collection will be monitored by a research coordinator through the Department of Orthopaedic Surgery. The research coordinator will be responsible for arranging follow-up care and confirming that postoperative MRI, functional tests, and patient-reported outcome measure are completed. The safety profile including laboratory tests and body composition will be performed under the guidance and monitoring of [name] based on his extensive knowledge of the anabolic steroid field. The body composition measurements will be made in [name]

Protocol Number: APP-17-01020

Version Date: 9/1/2017

laboratory. Postoperative rotator cuff repair rehabilitation and patient-reported outcome data will be overseen by [name], given her career-long expertise in shoulder-specific rehabilitation and shoulder pathology patient-reported outcome measures. In addition, patient recruitment will not be an issue as the study-eligible population significantly overlaps with the patient population most frequently affected by symptomatic, chronic rotator cuff tears.

Key Personnel

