4.0 Drug Information

Oxandrolone is an orally administered synthetic derivative of the hormone testosterone, and is classified as an anabolic steroid. In males, testosterone has many vital functions such as the development and support of reproductive organs, increased skeletal muscle mass, bone mineral density, and growth of facial and body hair.

Oxandrolone is approved by the Federal Drug Administration (FDA) in patients who have lost weight resulting from extensive surgery, severe trauma, chronic infection, or as an adjunctive therapy to promote weight gain. It is also approved for bone pain associated with osteoporosis, and to attenuate protein catabolism associated with the prolonged use of corticosteroids. Oral administration of Oxandrolone has demonstrated increases in lean mass, protein synthesis, and wound healing with no long-term adverse events in trauma patients as well as healthy male controls.¹⁻³ Elevated liver transaminase levels have been noted but have been transient and asymptomatic.¹⁻³ The aforementioned safety and efficacy profile of oral Oxandrolone makes it an appealing adjuvant treatment to counteract the major biologic consequences of a chronically torn rotator cuff (muscle atrophy, fatty infiltration, and intercellular fibrosis), which are known to lead to poor healing and diminished clinical outcomes.^{4,5}

Oxandrolone has been associated with the following side effects:

- Central Nervous System: Habituation, excitation, insomnia, depression, and changes in libido.
- Larynx: Deepening of the voice in females.
- Cardiovascular: Edema
- Breast: Gynecomastia.
- Hepatic: Cholestatic jaundice with, rarely, hepatic necrosis and death. Hepatocellular neoplasms and peliosis hepatis with long-term therapy (see US Boxed Warning below). Reversible changes in liver function tests also occur including increased bromsulphophthalein (BSP) retention, changes in alkaline phosphatase and increases in serum bilirubin, aspartate aminotransferase (AST, SGOT) and alanine aminotransferase (ALT, SGPT).
- Genitourinary: Inhibition of testicular function, testicular atrophy and oligospermia, impotence, chronic priapism, epididymitis, and bladder irritability.
- Hematologic: Bleeding in patients on concomitant oral anticoagulant therapy.
- Metabolic/Endocrine: Decreased glucose tolerance, increased creatinine excretion, increased serum levels of creatinine phosphokinase (CPK). Inhibition of gonadotropin secretion.

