- Fluid and Electrolytes: Retention of serum electrolytes (sodium chloride, potassium, phosphate, calcium).
- Musculoskeletal: Premature closure of epiphyses (in children).
- Dermatologic: Acne (especially in females and prepubertal males), hirsutism and male pattern baldness in females.
- Patients with moderate to severe COPD or COPD patients who are unresponsive to bronchodilators should be monitored closely for COPD exacerbation and fluid retention.

Contraindications: nephrosis, carcinoma of breast or prostate, hypercalcemia, pregnancy

US Boxed Warning:

Peliosis hepatitis: A condition in which liver, and sometimes, splenic tissue is replaced with blood-filled cysts which has occurred in patients receiving androgenic anabolic steroids. These cysts may be associated with hepatic dysfunction and even liver failure. This condition is usually completely reversible with cessation of drug.

Protocol Number: APP-17-01020

Version Date: 9/1/2017

Liver cell tumors: Most often benign and androgen-dependent, however, fatal malignant tumors have occurred. Withdrawal of the drug often results in regression or cessation of tumor progression. Hepatic tumors associated with androgens and anabolic steroids are much more vascular than other hepatic tumors and may be silent until life-threatening, intra-abdominal hemorrhage develops.

Blood Lipid Changes: Changes associated with increased risk of atherosclerosis are seen in patients treated with androgens or anabolic steroids, including decreased high-density lipoprotein (HDL) and increased low-density lipoprotein (LDL).

Pregnancy: Oxandrolone is classified as Category X in pregnancy due to teratogenic effects including embryotoxicity, fetotoxicity, infertility, and possible masculinization of the fetus.

Breast Feeding: It is unknown whether Oxandrolone is excreted in human milk. Because of the potential of serious adverse reactions in nursing infants from Oxandrolone, women who are nursing and do not wish to stop may not take part in the study.

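### Bleeding with oral anticoagulants is a named oxandrolone effect, but nothing provides for detecting or acting on an anticoagulant started during the 12 dosing weeks

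*Combined protocol and SAP*

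**What the plan says.** Among the side effects in section 4.0, under the hematologic heading, is "Bleeding in patients on concomitant oral anticoagulant therapy". The list of contraindications in the same section does not include anticoagulants: "Contraindications: nephrosis, carcinoma of breast or prostate, hypercalcemia, pregnancy".

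The exclusion criteria in section 5.0 include "Currently taking anticoagulation". They also exclude a DVT or myocardial infarction in the previous six months, coagulation disorders and congestive heart failure. The protocol does not say whether the anticoagulant exclusion is there because of the surgery or because of the drug.

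On timing, section 3.0 states: "Dosing will begin at the time of surgery and continue for 12 weeks". Table 1 in section 7.0 marks eligibility confirmation and medical history at the pre-procedure visit and on procedure day, and not afterwards.

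On safety oversight, section 7.0 says in general terms that safety measures are collected at the surgeon's routine visits. Section 3.0 is a little more specific: "The safety profile including laboratory tests and body composition will be performed under the guidance and monitoring" of an investigator experienced with anabolic steroids.

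Two exits are stated. Section 6.0 stops study drug after an adverse reaction to it and keeps the patient in follow-up. Section 3.0 covers altered rehabilitation, where the surgeon "will determine if the alteration in course warrants removal from the study".

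**The concern.** The protocol names the hazard, then controls it only up to the day exposure begins. Patients are 40 to 75 years old and have just had surgery, so a new indication for anticoagulation during the 12 weeks is plausible. If one arises, nothing requires anyone to ask about it and nothing says what to do with study drug. Under the stated stopping rule, drug continues until a reaction occurs.

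Blinding adds to this. Under section 5.0 the investigators receive the allocation list only at the end of the study, and the supplied text describes no unblinding for a medical need. The study team therefore could not tell a clinician who starts an anticoagulant whether the patient is taking oxandrolone. What is at stake is the safety of individual participants.

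**Working it through.** The plan gives no figure to reproduce. The check compares the hazard, the controls and the exposure window.

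**1. Exposure window.** Dosing runs from week 0 to week 12 (sections 3.0 and 6.0). Scheduled visits after surgery are at weeks 2, 6, 12, 24, 52 and 104 (section 7.0). Three of the six fall within or at the end of dosing. The week 12 visit comes when dosing ends, so only weeks 2 and 6 can change exposure. The longest stretch of dosing without a scheduled visit is 12 - 6 = 6 weeks, half of the treatment period.

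**2. Controls before dosing.** Eligibility is confirmed, and medical history taken, up to procedure day. A patient already on an anticoagulant should be caught here.

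**3. Controls during dosing.** Table 1 has 15 event rows. Five end by procedure day: consent, demographics, eligibility, medical history and randomization. The other 15 - 5 = 10 have a mark at week 2, 6 or 12: vital signs, testosterone and oxandrolone levels, liver enzymes, three MRI rows, body composition, questionnaires, range of motion and strength. None of the 10 is described as recording medicines or testing coagulation.

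The table is not a complete list of procedures. The monthly pregnancy test in section 3.0 has no row, and section 6.0 sets liver enzymes at weeks 6 and 12, which the table does not mark. The row count is therefore only supporting evidence. The main evidence is the text of sections 3.0 to 9.0 as supplied, which contains no medication review during dosing, no list of medicines prohibited on treatment and no instruction for a newly started anticoagulant.

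**4. Action rules.** The section 6.0 rule is triggered by a reaction, not by a new co-medication. The section 3.0 exit is triggered by a change in rehabilitation. Neither applies when an anticoagulant is started without a bleed.

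**5. Who is exposed.** Allocation is 1:1, so of 116 planned patients 116 / 2 = 58 receive oxandrolone. The daily dose is 2 x 12 = 24 mg in men and 2 x 6 = 12 mg in women.

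**6. How often.** The documents give no rate of new oral anticoagulant use and no bleeding rate under co-exposure. No event count follows.

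**7. How the plan treats its other hazards.** Hepatic risk is followed into dosing with repeated liver enzymes, and pregnancy risk with monthly tests and contraception. The anticoagulant interaction has an entry check only.

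**The case against.** The strongest reply is that the risk is already small. Besides current anticoagulation, section 5.0 removes patients with recent DVT, coagulation disorders, recent myocardial infarction and heart failure, some of the people likelier to need an anticoagulant. Half of those who remain take placebo. This stands, and it is why the point is not rated higher.

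A second reply is that somebody would notice. The surgeon collects safety measures at each visit, a therapist supervises rehabilitation and its logs are reviewed, some women have monthly pregnancy tests, and the trial is to follow Good Clinical Practice. These contacts make informal detection possible, including after week 6. None of them requires the question or prescribes an action.

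A third is that a hold is one choice among several. Closer monitoring or clinical judgment could also be defended, and the documents do not rank these options. That is fair. The case for a hold is that it agrees with the trial's own entry exclusion and needs no unblinding.

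A reader might go further in three ways that the documents do not support:
- *That co-administration breaches a stated contraindication.* Anticoagulants are not on that list.
- *That any patient who starts an anticoagulant would be on 24 mg/day of oxandrolone.* This is true only of men in the active arm.
- *That the untested dose in men raises this particular risk.* Section 1.0 says adverse events are typically dose-dependent, but says nothing about dose and the anticoagulant interaction.

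Finally, the consent form was not available and may already ask patients to report new medicines. That would cover part of the detection gap but would not supply a rule for study drug.

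**Conclusion.** The gap is real and should be closed. An anticipated drug interaction has an entry check, but no specified detection or response during the 12 weeks in which it could cause harm, and the one rule for stopping drug acts after the harm. It is a participant-safety point of moderate weight: probably infrequent, possibly serious, and cheap to address. It does not bear on the primary analysis, and no number of events, or of events prevented, is claimed.

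The conclusion assumes that the removed pages, including the consent form, contain no hold rule, and that no separate medication log exists outside the protocol. Confidence is medium for that reason.

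**What to change.** Make three changes:
1. Ask about newly started anticoagulants at the existing week 2 and week 6 visits, and show this in Table 1.
2. Instruct patients to report a new anticoagulant at once, unless the consent form already does so. This matters most after week 6, when no scheduled visit remains before dosing ends.
3. State in section 6.0 that study drug is held in either arm while an oral anticoagulant is taken, without unblinding and with outcome follow-up continued, as that section already provides after an adverse reaction. The text should also say whether dosing may resume once the anticoagulant stops.

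A week 12 question would come too late to alter exposure. Checks on androgens or testosterone-modifying drugs would do nothing for the bleeding hazard, so this point does not call for them.

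**Cost.** At most 116 x 2 = 232 short checks, all at visits already scheduled, plus a brief amendment. A few patients may stop drug early. Planned active dosing is 58 x 12 = 696 patient-weeks, so each active patient held gives up at most 12 / 696 = 1.7% of it.
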